#### **3.5.5 Modified Full Analysis Set**

The Modified Full Analysis Set (MFAS) will consist of all participants in the FAS, excluding any participant who received a mean dose more than  $\pm 10\%$  (ie excluding any participant who received a mean dose of IMP  $>10\%$  or  $<-10\%$ ) from the randomized (intended) dose.

The definition of the randomized dose as well as details for calculations are provided in Section 10.1.

#### **3.5.6 Per Protocol Set**

The Per-Protocol Set (PPS) is a subset of the FAS, consisting of those participants who had no important protocol deviation affecting the primary efficacy variable, as confirmed during a preanalysis data review meeting conducted prior to study unblinding. Post-Baseline deviations will not necessarily lead to total exclusion of a participant from the PPS but may lead to exclusion of specific data.

Analysis of the primary efficacy variable will be repeated using the PPS.

#### **3.5.7 Pharmacokinetic Per-Protocol Set**

The Pharmacokinetic Per-Protocol Set (PK-PPS) is a subset of the SS, consisting of those participants who had no important protocol deviation affecting the plasma concentration of rozanolixizumab. Post-Baseline deviations will not necessarily lead to total exclusion of a participant from the PK-PPS but may lead to exclusion of specific data.

#### **3.5.8 Pharmacodynamic Per-Protocol Set**

The Pharmacodynamic Per-Protocol Set (PD-PPS) is a subset of the FAS, consisting of those participants who had no important protocol deviation affecting the serum concentrations of total IgG, IgG subclasses, or neurofilament light chain. Post-Baseline deviations will not necessarily lead to total exclusion of a participant from the PD-PPS but may lead to exclusion of specific data.

### **3.6 Treatment assignment and treatment groups**

Safety and efficacy analyses will be based on the actual treatment participants received. Analyses will be performed by treatment groups and for all participants (if applicable) as described in Section 3.1.

### **3.7 Center pooling strategy**

It is planned to recruit participants in Europe, United States of America and Canada in this study, with possible extension to other regions and countries. There will be no stratification by site or country performed.

### **3.8 Coding dictionaries**

Adverse events (AEs) will be coded using version 22.0 or later of the Medical Dictionary for Regulatory Activities (MedDRA®).

Prior and concomitant medications will be coded according to version Sep 2017 or later of the World Health Organization Drug Dictionary (WHODD). Medical procedures will not be coded. If newer dictionary versions become available, data will be coded according to the approved internal standard dictionary management processes.

### **3.9 Changes to protocol-defined analyses**

- The definition of the SS has been updated to include all subjects who received at least one dose of the IMP.
- FAS definition:
  - Study participants will be analysed as actually treated only if they received the incorrect treatment for the entire study period. In case of partial mistreatment, the participant will be analyzed as randomized.
  - The FAS definition is clarified being limited to valid primary efficacy results up to V17 only as the primary efficacy endpoint is the change in iRODS from baseline to V17.
- To prevent bias in efficacy evaluation, an efficacy assessment is considered invalid, if that assessment follows the first intake of rescue medication. Assessments on the same day as first intake of rescue medication are valid.
- The protocol specifies the primary efficacy analysis covariate “prior Ig therapy” in section 14.3.1. Prior Ig therapy is defined by the stratification factor route of administration of prior Ig therapy.
- The MFAS was included as an additional analysis set in the SAP and was not part of the final clinical study protocol (CSP). This was added as the sensitivity analysis, to ensure the robustness of the efficacy analysis results in relation to dose variation, as foreseen in the CSP.
- Hy’s Law, defined in the protocol as

**$\geq 3 \times \text{ULN}$  ALT or AST with coexisting  $\geq 2 \times \text{ULN}$  total bilirubin in the absence of  $\geq 2 \times \text{ULN}$  ALP**

will instead be defined as

**(ALT or AST increase  $> 3 \times \text{ULN}$ ) and Total bilirubin  $> 2 \times \text{ULN}$  and ALP  $< 2 \times \text{ULN}$**   
to match program standards and general medical definitions.

- The study variable “Change in CIDP-specific auto-antibody levels in serum from Baseline during Treatment and Observation Periods” will not be analyzed in scope of this SAP. Sampling dates are captured in the CRF and will be listed. The samples’ results will not be part of this study’s database and instead analyzed and reported separately. The same is true for exploratory biomarkers RNA, proteins and metabolites variables.

### **3.9.1 Changes related to COVID-19**

With the event of the COVID-19 pandemic, an additional protocol deviation category (related/not related to COVID-19) has been introduced as well as an eCRF page "COVID-19 Impact" to identify visits and procedures which may have been impacted. These will be presented in the analysis results as described in Section 5.2.

Protocol deviations will be presented by COVID-19 period (pre- or during). A post- COVID-19 period may be added if applicable.

### **3.9.2 Interim Analysis**

An interim analysis was planned according to protocol section 14.7 Planned interim analysis and data monitoring:

*“The fourth and final interim analysis will be performed once all subjects have attended Visit 17, the first visit of the Observation Period (ie, Day 85). This interim analysis will provide, at a minimum, the results for the primary variable “Change from Baseline to Week 13 (Day 85) in iRODS score.”*

The event of all participants having attended Visit 17 is expected to coincide with the event of the last participant attending his/her last visit in CIDP01, resulting in database lock and the final analysis. With both triggers resulting in similar data, the interim analysis specified in the Interim Analysis SAP is not expected to provide additional value and will not be performed.

## **4 STATISTICAL/ANALYTICAL ISSUES**

### **4.1 Adjustments for covariates**

The regression analysis model for efficacy evaluation will adjust for the following covariates:

- Baseline score
- Route of administration of prior Ig therapy

### **4.2 Handling of dropouts or missing data**

#### **4.2.1 Efficacy data**

For participants who prematurely withdraw for any reason before Week 13 (Day 85), data collected during the PEOT Visit will be used to impute iRODS, INCAT and grip strength at the closest missing visit. In case a participant discontinues the study prematurely, the assessment of the PEOT visit will be mapped to closest missing visit according to the visit schedule utilizing the relative day in study to a maximum of day 85 (Visit 17). However, if a participant receives rescue medication prior to the PEOT visit, the assessment will be regarded invalid and only listed. Assessments on the same day as first intake of rescue medication is acceptable for analysis.

Since the analysis is based on the mixed model repeated measures (MMRM) approach, visits beyond the PEOT Visit will not be imputed. Missing data in-between visits will be covered by the MMRM approach.

For additional analyses of iRODS score to account for missing data, last observation carried forward (LOCF) and multiple imputation will be applied to address the issue of missing scores (see Section 8.1.3). There will be no imputation of missing individual item scores in the summaries for the iRODS; only to the overall iRODS score.

For the analysis of relapse data, participants who withdraw from the study for any reason before Week 13 (Day 85) or who have missing data at Week 13 (Day 85) will be considered as relapsed and analysed as such. The same is true for participants administered an Ig infusion rescue medication during this time interval.

Participants are asked to record three grip strength score assessments at each day. The efficacy parameter will be derived from grip strength scores taken by a participant up to five days prior to the first IMP (for Baseline value) or visit date (for post Baseline visit value):

1. Maximum of grip strength assessments available at a particular day
2. Mean of maximum grip strength over most recent three non-missing days - up to a maximum of five days
3. Missing values: In case all three assessments of a day are missing, the maximum grip strength score will be set to missing and will not be used for the derived score. In this case the preceding day's maximum grip strength score will be used instead, but no later than the fifth day prior to the first IMP or visit date respectively. In case data is entirely missing during the last five days prior to the visit, the derived score will be set to missing and the issue will be covered by the MMRM approach.

Sensitivity analyses will be performed for the primary efficacy parameter, as described in Section 8.1.3.

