### **7.7.3      Rescue medication**

If, at any time during the Treatment and Observation Period, the subject relapses according to the predefined criteria for relapse as specified in Section [4.1.2](#) using the subject's score on iRODS, INCAT, or maximum grip strength (assessed by site personnel), and supported by the medical judgement of the investigator, then rescue medication must be considered and the subject will be withdrawn from IMP (see Section [6.4](#)). The subject will return to the SOC Ig treatment (eg, IVIg of 2g/kg) as rescue medication at the time of relapse at the discretion of the investigator. The subject will have the opportunity to be stabilized over a period of 2 weeks to maximum 12 weeks starting from the relapse visit (ie, PEOT or later visit; see Section [8.3](#)). Once stabilized, the subject who completed the Treatment Period with no CIDP relapse, will be offered the possibility to enter in the OLE (CIDP04) and be treated with rozanolixizumab from that moment onward. The subject will complete the FV (V21) and enter the OLE on the same day. If a subject relapses during Treatment Period or does not wish to enter the OLE, the subject will continue their SOC treatment after stabilization. They will continue the stabilization visit schedule (every 1 to 3 weeks) until they have a follow-up of 12 weeks after last IMP dose.

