#### **3.5.4 Full Analysis Set**

The Full Analysis Set (FAS) will consist of all participants in the SS, who have a Baseline and at least one valid post-Baseline iRODS measurement up to Visit 17/PEOT (inclusively).

Measurements are considered invalid if the participant received rescue medication before the assessment of iRODS. Assessments collected at the same day as first intake of rescue medication are considered valid. Invalid measurements will not be used for summary tables and MMRM, but kept in listings.

The FAS is the primary analysis set for efficacy analyses. In the case of mistreatment, participants will be analyzed as treated if the participant received the incorrect treatment for the entire study period. In the case of partial mistreatment, patients should be analyzed as randomized, but considered as protocol violators. As for the SS, in the case of mistreatment participants will be primarily analyzed as treated. However, if applicable, sensitivity analyses will also be performed according to the randomized treatment group.

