#### **4.3 Handling of measurements obtained at the premature end of treatment visit**

Participants who withdraw from the study prematurely will be encouraged to return for the PEOT visit. The following rules will apply with regard to the inclusion of the results obtained at the PEOT in the descriptive summaries:

- Any measurements (including efficacy, safety, immunological and PD assessments) conducted at the PEOT should be included in the summaries for the respective scheduled visit, if the PEOT occurs at the time of the next scheduled visit (within the tolerance window specified in the protocol).
- If the PEOT does not correspond to the day of a scheduled visit, the efficacy, safety and other relevant assessments of the PEOT should be mapped to the nearest scheduled visit, relative to the Baseline visit date, following the last scheduled visit where assessments are available.
- If the date of the PEOT is equidistant between 2 scheduled visits at which no scheduled assessments were performed, the assessments from the PEOT will be mapped to the earliest of these visits.

Different domains from the same PEOT may be re-assigned to different study visits depending on the study schedule of assessments ie, measurements obtained at the PEOT can only be mapped to a scheduled visit at which the respective assessment was intended to be measured. Assessments from the PEOT that are mapped to scheduled visits will be flagged in the data listings.

Visits after the PEOT following the schedule of the 12-Weeks Observation period, will be mapped to the corresponding planned visit. Assessments on these visits will be flagged in the data listing.

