## 8 EFFICACY ANALYSES

All analyses of the efficacy variables will be performed on the FAS. Additional outputs may be repeated for the PPS or the MFAS where indicated. Listings will be based on the SS.

Treatment group assignment for efficacy analysis will be according to the actual treatment regimen.

All efficacy analyses are to be interpreted as exploratory analyses. No p-values will be presented.

Any efficacy measurements are considered invalid, if the participant received rescue medication before the assessment. Assessments collected at the same day as first intake of rescue medication are considered valid. Respective measurements will not be used for summary tables and MMRM, but kept in listings. This includes iRODS, INCAT, clinician reported grip strength, RT-MRC, CIDP PRO and Fatigue, PGIS, PGIC and the patient reported grip strength as derived in Section 8.2.4.

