### 8.2.9 Use of rescue medication

The percentage of participants with concomitant medication identified as rescue medication [Yes/No] in the eCRF and time to first rescue medication administration will be summarized by treatment group and for all participants and listed by treatment group at each scheduled assessment during the Treatment and Observation Period.

If a participant receives rescue medication at multiple times, the relative day of the first occurrence is used to define the time to rescue medication.

The statistical methods applied to use of rescue medication and time to use of rescue medication will be the same as for CIDP relapse (iRODS), see Sections 8.2.1 and 8.2.1.1. The rule for handling missing data is described in Section 4.2.7.

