## 10.2 Adverse events

Adverse events will be recorded from the time of informed consent until study completion. All AEs will be coded (Section 3.8) and categorized by relationship to rozanolixizumab.

In addition, AEs will be classified according to the Common Terminology Criteria for Adverse Events (CTCAE) Version 5.0 for severity. For any AEs where it is not possible to provide a CTCAE grading, the events will be assessed using a standard intensity classification (mild, moderate and severe).

A TEAE is defined as any event that was not present prior the first administration of IMP or any unresolved event already present before the first administration of IMP that worsens in intensity following exposure to treatment until 8 weeks following the last administration of IMP. Adverse events starting before the first administration of IMP or later than 8 weeks after the administration of the last IMP will not be considered TEAEs. Such events will be listed only.

Where dates are missing or partially missing, AEs will be assumed to be treatment-emergent unless evidence exists that does not allow the AE to be treatment-emergent. Handling of missing dates/times for classification of AEs as TEAEs is described in Section 4.2.7.

The following rules will be used to assign a TEAE to the study periods:

1. **Treatment Period:** a TEAE will be assigned to the Treatment Period for the tabulations if the start date/time of the event is at the time of or after the first administration of IMP on Day 1, up to Visit 17/PEOT (non-inclusively).
2. **Observation Period:** a TEAE will be assigned to the Observation Period for the tabulations if the start date/time of the event is at or after Visit 17/PEOT till 8 weeks after administration of the last IMP.
  - The Observation Period's TEAEs will be stratified by TEAEs of participants who received/did not receive standard of care treatment (i.e. Ig treatment) between start of the Observation Period and occurrence of the TEAE.

The number and percentage of participants who experience TEAEs will be summarized by Treatment Period, Observation Period (standard of care treatment status identified by WHODD J06BA01 and J06BA02) and Overall with respective treatment group. The following summaries will be presented:

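### Efficacy scores are voided only after medication flagged as rescue, so a PEOT score taken after unflagged immunoglobulin or plasma exchange stays in the primary MMRM

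*SAP*

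**What the plan says.** Four places in the SAP void efficacy values, and all four use the same trigger.

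- SAP 3.5.4 (Full Analysis Set): "Measurements are considered invalid if the participant received rescue medication before the assessment of iRODS".
- SAP 3.9 (changes to the protocol's analyses), which also gives the reason: "To prevent bias in efficacy evaluation, an efficacy assessment is considered invalid, if that assessment follows the first intake of rescue medication".
- SAP 4.2.1 (PEOT visit): "However, if a participant receives rescue medication prior to the PEOT visit, the assessment will be regarded invalid and only listed".
- SAP 8 (all efficacy variables): "Any efficacy measurements are considered invalid, if the participant received rescue medication before the assessment".

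Scores from the same day as the first rescue intake stay valid. SAP 8.2.9 shows how rescue is recognised: "concomitant medication identified as rescue medication [Yes/No] in the eCRF". Protocol 7.7.3 says what it is: "The subject will return to the SOC Ig treatment (eg, IVIg of 2g/kg) as rescue medication at the time of relapse".

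A PEOT score that is not voided enters the analysis. SAP 4.2.1 assigns it to the closest missing visit, up to Day 85. Under SAP 4.3, where the PEOT falls on no scheduled day, "the efficacy, safety and other relevant assessments of the PEOT should be mapped to the nearest scheduled visit".

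**The concern.** The trial takes Ig-dependent participants off Ig. A score taken after Ig has restarted no longer compares rozanolixizumab with placebo alone, and the sponsor accepts this by voiding scores after rescue Ig. As written, though, validity depends on how the medication was labelled, not on what the participant received. Ig labelled rescue removes the score; Ig labelled as a return to standard of care does not. PLEX, which Protocol Section 2 also lists as effective in CIDP, is not covered unless a site happens to flag it. What is at stake is the primary estimate and its 90% CI, since SAP 8 reports no p-values.

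**Working it through.** **1. Can Ig precede the PEOT score without a rescue flag?** Protocol Table 8-1 has a row for withdrawal for reasons other than relapse. It marks stabilization with rescue medication as no, yet returns the participant to Ig. Protocol 8.4 ties the PEOT visit to the date of the withdrawal decision, as near as can be arranged. No sentence makes the PEOT assessment a condition for restarting Ig. Ig taken between the decision and the visit would be standard of care, not rescue.

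**2. Can PLEX?** Protocol 6.4, under mandatory IMP discontinuation, lists PLEX in item 4 and rescue or relapse in item 5, so the protocol treats them as different events. Item 4 covers both needing and taking PLEX. Where taking it is what stops IMP, the PEOT visit comes afterwards. PLEX may also be recorded as a procedure: Protocol Table 5-1 collects procedures separately, SAP 3.8 leaves them uncoded, and the flag in SAP 8.2.9 belongs to a medication. The documents do not say which form holds PLEX.

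**3. Where does the score go?** If the PEOT maps to Visit 17, it enters the Day 85 contrast directly. If it maps earlier, it reaches Day 85 only through the modelled covariance. The LOCF analysis (SAP 8.1.3.2) gives no protection, because it would carry such a score forward to Day 85.

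**4. Is there another filter?** The Per-Protocol Set may exclude specific data (SAP 3.5.6), but that analysis is supportive. No rule acts on the FAS.

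**5. Could the SAP recognise unflagged Ig?** Yes. For adverse events in the Observation Period, SAP 10.2 uses "standard of care treatment status identified by WHODD J06BA01 and J06BA02".

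**6. Scale.** The plan gives no count of such cases, so the effect cannot be computed. The following only shows what one value can weigh.

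The plan's own figures first (SAP 2.4): n = 15 per group, one-sided alpha 0.05, effect size d. Power = P(T > t(0.95, 28)), with T noncentral t on 28 degrees of freedom and noncentrality d × √(15/2).

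- d = 0.93: noncentrality 2.547, power 79.9% (stated 80%).
- d = 0.52: noncentrality 1.424, power 39.9% (stated 40%).
- 30 / 0.9 = 33.3, rounded up to 34 randomized, as stated.

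Assumption, not taken from the documents: k of 15 placebo participants have a Day 85 score at which Ig or PLEX recovers a fraction f of the full treatment effect, with the SD unchanged. Then d = 0.93 × (1 − k × f / 15).

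| k | d (f = 1) | power (f = 1) | power (f = 0.5) |
|---|---|---|---|
| 0 | 0.930 | 79.9% | 79.9% |
| 1 | 0.868 | 75.0% | 77.5% |
| 2 | 0.806 | 69.4% | 75.0% |
| 3 | 0.744 | 63.4% | 72.3% |

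One fully recovered score moves the standardized difference by 0.93 / 15 = 0.062. In the rozanolixizumab arm, a score raised by Ig would move it the other way. k = 0 is a realistic value.

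**The case against.** The best defence is that the protocol's sequence already handles this. Table 8-1 lists the PEOT visit before the return to standard of care. SAP 6.4.2 and 10.2 start the Observation Period, in which that return is allowed, at Visit 17/PEOT. Protocol 7.7.2 prohibits Ig during treatment and points to the rescue section, so sites may flag any early Ig as rescue. The eCRF guidelines are not in the documents and may define the flag broadly. Deviations are reviewed before unblinding, concomitant medications are listed with dates, and efficacy is exploratory. All of this stands and makes affected values few. It does not close the gap: the sequence is implied, not required, and the SAP itself defines no wider flag.

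A defence that scores should count whatever was taken is not open here, because the sponsor has already rejected it for rescue Ig.

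Several stronger readings are tempting and are not supported:

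- That intake of a prohibited therapy always precedes the PEOT. Protocol 6.4 and 7.7.2 also trigger the stop on need alone, so a PEOT before therapy is equally provided for.
- That dexamethasone, rituximab and other biologics belong in the same rule. Protocol Section 2 names steroids as effective only at high dose and does not name rituximab. Prednisolone up to 30 mg/day is permitted (Table 7-3), and iv corticosteroids are recommended for severe infusion reactions (Table 18-1). Voiding all later scores after any such drug, for any indication, would discard data without a matching reason.
- That completers are affected. The protocol starts the Observation Period after Visit 16, but completing treatment includes Visit 17, so elective Ig is naturally read as starting after that visit.
- That IMP stops for headache in the earlier myasthenia gravis study size the problem. They count stops, not Ig before a PEOT score, and this trial allows dose reduction for persistent headache.

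**Conclusion.** The point holds as an inexpensive improvement to the SAP, not as a demonstrated bias. On the text, a score taken after unflagged Ig or PLEX and before or at the PEOT assessment remains in the primary MMRM, which does not fit the purpose given in SAP 3.9. The conclusion assumes that the flag follows Protocol 7.7.3; if the eCRF guidance flags all Ig and PLEX as rescue, the gap closes in practice. The count of affected values cannot be obtained from the documents and may be zero. The direction depends on the arm in which they fall. The power figures above rest on an assumed k and should not be read as an expected loss.

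**What to change.** Change the SAP only. In 3.5.4, 3.9, 4.2.1 and 8, treat as invalid any efficacy value up to Visit 17/PEOT that follows the first intake, after the first IMP dose, of any Ig (WHODD J06BA01 or J06BA02) or of PLEX or immunoadsorption, whether or not it is flagged as rescue. Keep same-day values valid, as now. Do not void Observation Period values taken on elective Ig; tabulate them by standard-of-care status, as SAP 10.2 does for adverse events.

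Cost: no new data collection and no protocol amendment. A few values may move to listings, and the MMRM then relies on its missing-data assumption for them. A participant whose only post-Baseline score is voided would leave the FAS. Because procedures are not coded, someone must check the recorded procedures by hand for PLEX and immunoadsorption, which is a short task with 34 participants.
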